Appendix G: 10-Meter Walk Test

Meter 0 Meter 2
Start
Walk Start
Timing

Meter 8 Meter 10
End
Timing End
Walk

1. Subjects will walk with/without assistance for 10 meters.
2. Time will be measured for the intermediate 6 meters to allow for acceleration and deceleration.
3. Timing will start when the toes of the leading foot crosses the 2-meter mark.
4. Timing will stop when the toes of the leading foot crosses the 8-meter mark.
5. Assistive devices can be used but should be kept consistent and documented from test to test.
6. Collect two trials at the subject's comfortable walking speed, followed by two trials at their fast-walking speed.
7. Trials for each speed will be averaged.

Appendix H: 6-Minute Walk Test

1. A “warm-up” period before the test should not be performed.
2. The patient should sit at rest in a chair, located near the starting position, for at least 10 minutes before the test starts.
3. During this time, check for contraindications, and make sure that clothing and shoes are appropriate.
4. Instruct the subject as follows:

“The object of this test is to walk as far as possible for 6 minutes. You will walk back and forth in this hallway. Six minutes is a long time to walk, so you will be exerting yourself. You will probably get out of breath or become exhausted. You are permitted to slow down, to stop, and to rest as necessary. You may lean against the wall while resting, but resume walking as soon as you are able.

You will be walking back and forth around the cones. You should pivot briskly around the cones and continue back the other way without hesitation. Now I’m going to show you. Please watch the way I turn without hesitation.”

Demonstrate by walking one lap yourself. Walk and pivot around a cone briskly.

“Are you ready to do that? I am going to use this counter to keep track of the number of laps you complete. I will click it each time you turn around at this starting line. Remember that the object is to walk AS FAR AS POSSIBLE for 6 minutes, but don’t run or jog.

Start now, or whenever you are ready.”

5. Position the patient at the starting line. You should also stand near the starting line during the test. Do not walk with the patient. As soon as the patient starts to walk, start the timer.
6. Do not talk to anyone during the walk. Use an even tone of voice when using the standard phrases of encouragement. Watch the patient. Do not get distracted and lose count of the laps. Each time the participant returns to the starting line, click the lap counter once (or mark the lap on the worksheet). Let the participant see you do it. Exaggerate the click using body language, like using a stopwatch at a race.
7. Record the number of laps from the counter.
8. Record the additional distance covered (the number of meters in the final partial lap) using the markers on the wall as distance guides. Calculate the total distance worked, rounding to the nearest meter.
9. Congratulate the patient on good effort and offer a drink of water.

Appendix I: Five Times Sit to Stand Test

1. To perform the test, the person must sit in a chair, with arms crossed over their chest with their back resting on the back of the chair.
2. The chair should have a straight back, and it is recommended it have a height between 43-46 cm.
3. When ordered, the subject should stand up completely and then return to the sitting position during 5 repetitions, performing this activity as fast as possible.
4. Subjects will be timed from the initial sitting position to the final standing position.

Appendix J: Short Form-36

Please answer the 36 questions of the **Health Survey** completely, honestly, and without interruptions.

GENERAL HEALTH:

In general, would you say your health is:

Excellent Very Good Good Fair Poor

Compared to one year ago, how would you rate your health in general now?

Much better now than one year ago
 Somewhat better now than one year ago
 About the same
 Somewhat worse now than one year ago
 Much worse than one year ago

LIMITATIONS OF ACTIVITIES:

The following items are about activities you might do during a typical day. Does your health now limit you in these activities? If so, how much?

Vigorous activities, such as running, lifting heavy objects, participating in strenuous sports.

Yes, Limited a lot Yes, Limited a Little No, Not Limited at all

Moderate activities, such as moving a table, pushing a vacuum cleaner, bowling, or playing golf

Yes, Limited a Lot Yes, Limited a Little No, Not Limited at all

Lifting or carrying groceries

Yes, Limited a Lot Yes, Limited a Little No, Not Limited at all

Climbing several flights of stairs

Yes, Limited a Lot Yes, Limited a Little No, Not Limited at all

Climbing one flight of stairs

Yes, Limited a Lot Yes, Limited a Little No, Not Limited at all

Bending, kneeling, or stooping

Yes, Limited a Lot Yes, Limited a Little No, Not Limited at all

Walking more than a mile

Yes, Limited a Lot Yes, Limited a Little No, Not Limited at all

Walking several blocks

Yes, Limited a Lot Yes, Limited a Little No, Not Limited at all

Walking one block

Yes, Limited a Lot Yes, Limited a Little No, Not Limited at all

Bathing or dressing yourself Yes, Limited a Lot Yes, Limited a Little No, Not Limited at all**PHYSICAL HEALTH PROBLEMS:**

During the past 4 weeks, have you had any of the following problems with your work or other regular daily activities as a result of your physical health?

Cut down the amount of time you spent on work or other activities Yes No**Accomplished less than you would like** Yes No**Were limited in the kind of work or other activities** Yes No**Had difficulty performing the work or other activities (for example, it took extra effort)** Yes No**EMOTIONAL HEALTH PROBLEMS:**

During the past 4 weeks, have you had any of the following problems with your work or other regular daily activities as a result of any emotional problems (such as feeling depressed or anxious)?

Cut down the amount of time you spent on work or other activities Yes No**Accomplished less than you would like** Yes No**Didn't do work or other activities as carefully as usual** Yes No**SOCIAL ACTIVITIES:**

Emotional problems interfered with your normal social activities with family, friends, neighbors, or groups?

 Not at all Slightly Moderately Severe Very Severe**PAIN:**

How much bodily pain have you had during the past 4 weeks?

 None Very Mild Mild Moderate Severe Very Severe

During the past 4 weeks, how much did pain interfere with your normal work (including both work outside the home and housework)?

 Not at all A little bit Moderately Quite a bit Extremely

CIONIC

CIONC FOR ORTHOPEDICS

ENERGY AND EMOTIONS:

These questions are about how you feel and how things have been with you during the last 4 weeks. For each question, please give the answer that comes closest to the way you have been feeling.

Did you feel full of pep?

- All of the time
- Most of the time
- A good Bit of the Time
- Some of the time
- A little bit of the time
- None of the Time

Have you been a very nervous person?

- All of the time
- Most of the time
- A good Bit of the Time
- Some of the time
- A little bit of the time
- None of the Time

Have you felt so down in the dumps that nothing could cheer you up?

- All of the time
- Most of the time
- A good Bit of the Time
- Some of the time
- A little bit of the time
- None of the Time

Have you felt calm and peaceful?

- All of the time
- Most of the time
- A good Bit of the Time
- Some of the time
- A little bit of the time
- None of the Time

Did you have a lot of energy?

- All of the time
- Most of the time
- A good Bit of the Time
- Some of the time
- A little bit of the time
- None of the Time

Have you felt downhearted and blue?

- All of the time
- Most of the time
- A good Bit of the Time
- Some of the time
- A little bit of the time
- None of the Time

Did you feel worn out?

- All of the time
- Most of the time
- A good Bit of the Time
- Some of the time
- A little bit of the time
- None of the Time

Have you been a happy person?

- All of the time
- Most of the time
- A good Bit of the Time
- Some of the time
- A little bit of the time
- None of the Time

Did you feel tired?

- All of the time
- Most of the time
- A good Bit of the Time
- Some of the time
- A little bit of the time
- None of the Time

SOCIAL ACTIVITIES:

During the past 4 weeks, how much of the time has your physical health or emotional problems interfered with your social activities (like visiting with friends, relatives, etc.)?

- All of the time
- Most of the time
- Some of the time
- A little bit of the time
- None of the Time

GENERAL HEALTH:

How true or false is each of the following statements for you?

I seem to get sick a little easier than other people

Definitely true

Mostly true

Don't know

Mostly false

Definitely false

I am as healthy as anybody I know

Definitely true

Mostly true

Don't know

Mostly false

Definitely false

I expect my health to get worse

Definitely true

Mostly true

Don't know

Mostly false

Definitely false

My health is excellent

Definitely true

Mostly true

Don't know

Mostly false

Definitely false

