Walking endurance (m) will be measured using the 6MWT using the same walkway utilized for the 10mWT. Participants will wear the Cionic Neural Sleeve during the two 6MWTs. For the 6MWT, the subject will be instructed to walk as far as possible for 6 minutes, up and down the pathway, and pivoting to turn at the end of each lap³¹. Timing will begin when the participant steps over the start line, and distance traveled will be recorded. Encouragement outlined in the guideline (Appendix C) will be given to the subjects after each minute, and participants will be instructed to stop at 6 minutes or prior, if they are unable to complete 6 minutes. Use of a walking aid and standing rests will be permitted. Normative values of people aged 40-80 years will be used as reference values³².

Secondary Measures

Adherence to Program

Adherence to the program will be measured by the usage log of the Cionic Neural Sleeve. The data collected from the Cionic Neural Sleeve worn on the affected limb/most affected limb will be recorded to monitor compliance to the program in number of repetitions and duration of walking.

Thigh Muscle Volume

Thigh muscle volume will be estimated using a measurement tape for thigh circumference and a prediction model. Thigh circumference (cm) will be measured from a point 15 cm proximal to the superior pole of the patella. The prediction model is as follows: Muscle volume (cm³)

=4226.3 – 42.5×age(year) – 955.7× gender(male=1, female=2) + 45.9×body weight(kg) + 60.0×thigh circumference(cm)³³. It was selected for this study for its correlation ($r^2 = 0.745$) to magnetic resonance imaging, the gold standard of measuring muscle volume³⁷.

Functional Ability of the Lower Limb

To measure functional ability of the lower limb, subjects will be asked to perform the FTSST. The FTSST requires participants to sit in a chair with their arms crossed over the chest and then to stand up/sit down for five times, as fast as possible³⁴. Subjects will be timed from the initial sitting position to the final standing position. Cut-off points of 10.8 and 12.8 seconds will be used as references for intermediate and poor function, respectively³⁵.

Quality of Life

The Short Form 36 (SF-36) is a generic measure of health status that measures self-reported functional health and well-being in the past four weeks in eight domains or two summary scores. Scores range from 0 to 100, with 0 representing extreme interference, and 100 representing no interference³⁶.

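### The first of the two SF-36 social-activity items in Appendix J asks only about emotional causes, has no recall period and ends in severity labels, so that domain could register a knee-related change at as little as half its size

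*Combined protocol and SAP*

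**What the plan says.** Quality of life is one of four secondary interests (Overview of Study). The questionnaires are given at baseline, at 6 weeks and at end of study (Tables 1 and 2). Data Analysis/Statistical Analysis covers every primary and secondary measure.

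The Quality of Life section says that the SF-36 "measures self-reported functional health and well-being in the past four weeks in eight domains or two summary scores". It adds: "Scores range from 0 to 100, with 0 representing extreme interference, and 100 representing no interference". It does not name the eight domains and gives no scoring rule.

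Appendix J is the form itself, introduced with "Please answer the 36 questions of the" survey. It has two items under SOCIAL ACTIVITIES headings:

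- The first reads in full "Emotional problems interfered with your normal social activities with family, friends, neighbors, or groups", with the options "Not at all Slightly Moderately Severe Very Severe".
- The second, after the energy and emotions block, begins "During the past 4 weeks, how much of the time has your physical health or emotional problems interfered with your social activities" and is answered on a five-level frequency scale.

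**The concern.** The two items share a heading but do not ask about the same thing. The first restricts the cause to emotional problems. The second admits physical causes as well and fixes the period.

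In knee osteoarthritis, physical limitation is a main expected route to social limitation. A participant whose knee stops all social activity, but who has no emotional difficulty, would answer the first item truthfully with *Not at all*, the best possible response. Any later improvement in the knee cannot raise that answer.

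At stake is the sensitivity of one domain of a secondary outcome, and of any summary score built on it. A further question is whether the result can be reported as the instrument named in the Quality of Life section. With about 45 participants in three groups (45/3 = 15 per group if equal), there is little sensitivity to spare.

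**Working it through.** **1. Is the item one of the 36?** Counting Appendix J block by block: general health 2, activity limitations 10, physical problems 4, emotional problems 3, social 1, pain 2, energy and emotions 9, social 1, general health 4. The sum is 2+10+4+3+1+2+9+1+4 = 36, which matches the number the form states. The item is therefore part of the set, and exactly two items concern social activity.

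**2. The items side by side**

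| Feature | First social item | Second social item | Quality of Life section |
|---|---|---|---|
| Cause named | emotional only | physical or emotional | not stated |
| Recall period | none | 4 weeks | four weeks |
| Question stem | none | how much of the time | – |
| Response labels | end in *Severe*, *Very Severe* | frequency | scale of interference |

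The first item's last two labels are the same as those of the bodily-pain severity item just below it. The form's pain-interference item ends in *Extremely*. No recall period carries over from a shared introduction, because the blocks before and after state their own.

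**3. Effect on the domain score.** The documents give no scoring, so three assumptions are needed:
- the domain is the equal-weight mean of the two items;
- each item is scored 0, 25, 50, 75 or 100;
- the first item picks up a fraction r of a knee-related change, with r between 0 and 1.

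The fraction of the change that the domain keeps is (1 + r)/2. For a knee-related change that would move two well-formed items by one level (25 points) each:

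| r | Domain change, 25 × (1 + r)/2 | Retained |
|---|---|---|
| 0 | 12.5 | 50% |
| 0.25 | 15.6 | 62.5% |
| 0.5 | 18.75 | 75% |
| 0.75 | 21.9 | 87.5% |
| 1 | 25 | 100% |

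Example at r = 0: with purely physical interference all of the time, the second item scores 0 and the first scores 100. The domain is (100 + 0)/2 = 50, where two well-formed items would give 0. With interference some of the time it is (100 + 50)/2 = 75 instead of 50.

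**4. Does this translate into power?** Only with further assumptions, because the item also changes the SD of the domain. Assume equal item SDs, r = 0, and a correlation of 0.6 between two well-formed items. Let ρ be the correlation between the items as printed. The standardised effect relative to the well-formed domain is 0.5 × √((1 + 0.6)/2) / √((1 + ρ)/2):
- ρ = 0.6: 0.50
- ρ = 0.3: 0.55
- ρ = 0: 0.63

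If instead the first item is constant at 100, the domain is (100 + X)/2, where X is the second item. Change and SD are then both halved, and the standardised effect is that of the second item alone: √((1 + 0.6)/2) = 0.89 of the well-formed value.

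**The case against.** Several objections carry weight.

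- **The form still captures knee-related limitation.** This stands. The second social item asks about it directly, so a reader who concludes that the form misses it goes too far. Only the first item does.
- **Half size is the worst case.** This stands. It needs equal weighting and no response at all from the first item. Neither is in the documents, and knee pain can affect mood, so r above 0 is plausible.
- **A reader might infer that about four times the participants would be needed.** The documents do not support this. A factor of 1/0.50² = 4 requires an item that does not respond to the knee and yet varies enough to leave the SD unchanged. With the item constant, the factor is 1/0.89², about 1.25. The answer turns wholly on assumed correlations. Appendix A sizes the trial on WOMAC metrics only, so no planned sample size is affected.
- **A missing recall period is not in itself a contradiction.** This stands in part. Other SF-36 items in Appendix J refer to health in general, to a year ago or to a typical day. The mismatch with the companion item remains.
- **The options are partly usable.** This stands. The first three labels can describe interference; only the top two fit badly.
- **The text may have lost a line when the PDF was read.** This cannot be excluded. It is unlikely: the fragment begins with a capital letter directly after its heading, the neighbouring items are intact, the count reaches 36, and a lost line would not explain the severity labels. A look at the live form settles it.
- **Importance is limited.** This stands. The hypotheses do not mention quality of life, no analysis of the social domain is specified, and function and pain are primary outcomes on separate WOMAC forms.

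**Conclusion.** The wording defect holds on the face of Appendix J. The first social-activity item differs from its companion in cause, recall period and stem, and its top labels do not fit the interference scale described in the Quality of Life section.

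Under an assumed equal-weight two-item score, a knee-related change in that domain is weakened by up to half. The range retained is 50% to 100%, and the documents do not say where in it the trial would fall. No sample-size multiplier should be quoted.

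The same form goes to all arms, so there is no reason to expect bias between them. The loss is of sensitivity in one domain of a secondary outcome, together with a score that is not that of the named instrument. It is worth correcting because the correction is cheap and a response not asked for at a visit cannot be recovered later.

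**What to change.** **Before further use:** check this item against the SF-36 source that the protocol cites (reference 36, the survey update), and check the rest of Appendix J in the same pass. Correct the item so that it covers physical as well as emotional causes over the last 4 weeks, with the response options of that source. The exact replacement wording must come from the source, because the protocol does not reproduce it. State the SF-36 scoring in the Quality of Life section at the same time.

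**If forms have already been collected:** label the social domain, and any summary score that uses it, as non-standard, and report the second social item separately.

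**Cost:** one corrected line on the form and an IRB notification, with no extra visits, staff or participants. The drawback is possible inconsistency between forms completed before and after the correction. A participant followed across the change would have a baseline and a final score from different forms, so the form version should be recorded at each visit.
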